### 9.6.3 Summaries of Baseline Characteristics, Demographics, and Other Analyses

The comparability of the treatment groups for each relevant characteristic will be assessed observationally; no statistical hypothesis tests will be performed on these characteristics. The number and percentage of participants screened, the primary reasons for screening failure, and the primary reason for discontinuation will be displayed. Demographic variables and baseline characteristics will be summarized by treatment group either by descriptive statistics or categorical tables.

## 9.7 Interim Analyses

No interim analyses are planned for this trial.

## 9.8 Multiplicity

The Type-I error rate over the two primary hypotheses will be controlled by the Hochberg procedure [Benjamini, Y. and Hochberg, Y. 1995]. The overall success is determined by a success of at least one hypothesis.

If the one-sided p-values for both primary hypothesis tests are  $< 0.025$ , then both tests will be declared successful. Otherwise, if the smaller of the p-values is  $< 0.0125$ , then only the hypothesis test associated with the smaller p-value will be declared successful.

## 9.9 Sample Size and Power Calculations

A total of approximately 450 participants (180 in Cohort A, 270 in Cohort B) will be randomized. The power computation has been performed conservatively based on the number of participants expected to have LDL-C data at Week 12. Assuming a drop-out rate of 10%, 162 participants (81 per arm) in Cohort A and 242 participants (121 per arm) in Cohort B will be available for the power calculation. The sample in Cohort A has a 93% power to demonstrate the superiority of MK-0653C 10/10 mg over atorvastatin 20 mg at a one-sided 2.5% alpha-level. The half-width of the 95% confidence interval for the between-treatment difference is expected to be 7.0%. Similarly, the sample in Cohort B has a 95% power to demonstrate the superiority of MK-0653C 10/20 mg over atorvastatin 40 mg at a one-sided 2.5% alpha-level. The half-width of the 95% confidence interval for the between-treatment difference is expected to be 5.7%. The overall power to success on at least one hypothesis is 99% at a 2.5% alpha-level with 88% power to succeed for both hypotheses. If only one hypothesis is successful according to Hochberg procedure, the sample in Cohort A will result in a power of 88% and the sample in Cohort B will result in a power of 91% at 1.25% alpha-level. The power and sample sizes are based on the following assumptions: the treatment difference in percent changes from baseline in LDL-C at Week 12 are 12.3% and 10.5%, and unconditional standard deviations are 22% and 23% for Cohorts A and B, respectively, according to P162 results from the ANCOVA model.

The safety power table displays a range of AE rates and the possible difference that can be detected with the sample size of the study at 90% and 80% power is shown in [Table 8](#). All calculations are based on 2-sided  $\alpha=0.05$  significance level.

Table 8 Safety Power Calculation

AE rate in Atorvastatin 20 mg or 40 mg Group	Percentage Point Difference in Cohort A (MK-0653C 10/10 mg- Atorvastatin 20 mg) Power of 80% (90%)	Percentage Point Difference in Cohort B (MK-0653C 10/20 mg- Atorvastatin 40 mg) Power of 80% (90%)
1%	10.3 (12.2)	8.2 (10.0)
2%	11.4 (13.5)	9.2 (11.1)
3%	12.3 (14.6)	9.9 (11.9)
AE = adverse event		

## 9.10 Subgroup Analyses

To determine whether the treatment effect is consistent across various subgroups, the estimate of the between-group treatment effect (with a nominal 95% CI) for the primary endpoints will be estimated within each category of the following classification variables:

- Age category (< 65,  $\geq$ 65 years)
- Gender (male, female)
- Baseline LDL-C ( $\leq$  or  $>$  median)
- Disease risk Category based on LDL-C (as in Section 4.1)

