## 9.1 Statistical Analysis Plan Summary

Key elements of the statistical analysis plan are summarized below; the comprehensive plan is provided in Sections 9.2-9.12.

Study Design Overview	A Phase III, Randomized, Double-blind Clinical Trial to Study the Efficacy and Safety of MK-0653C in Chinese participants with Hypercholesterolemia
Treatment Assignment	A double-blind/masking technique will be used. After the run-in period, 180 participants will be randomized in a ratio of 1:1 into the arms of MK-0653C 10/10 mg and atorvastatin 20 mg in Cohort A and 270 participants will be randomized in a ratio of 1:1 into the arms of MK-0653C 10/20 mg and atorvastatin 40 mg in Cohort B. Randomization will be stratified by disease risk category (low, moderate, high, very high) as defined in Section 4.1.
Analysis Populations	Efficacy: Full Analysis Set (FAS) Safety: All Participants as Treated (APaT)
Primary Endpoint	Percent change from baseline in LDL-C at Week 12
Secondary Endpoints	1. Percentage of participants with adverse events. 2. Change from baseline in laboratory parameters and vital signs at each visit 3. Percentage of participants discontinued from study medication
Statistical Methods for Key Efficacy Analyses	The primary hypothesis for each cohort will be evaluated by comparing MK-0653C to atorvastatin on the percent change from baseline in LDL-C using a constrained longitudinal data analysis (cLDA) model.
Statistical Methods for Key Safety Analyses	Counts and percentages of AEs will be provided. P-values and confidence intervals for the incidence of AEs of clinical interest will be estimated using the Miettinen and Nurminen method [Miettinen, Olli and Nurminen, Markku 1985].
Interim Analyses	No interim analyses are planned for this trial.
Multiplicity	The Type-I error rate over the multiple treatment comparisons will be controlled by the Hochberg testing procedure.
Sample Size and Power	A total of approximately 450 participants (180 in Cohort A, 270 in Cohort B) will be randomized. The sample in Cohort A has 93% power to demonstrate the superiority of MK-0653C 10/10 mg over atorvastatin 20 mg at a one-sided 2.5% alpha-level. Similarly, the sample in Cohort B has 95% power to demonstrate the superiority of MK-0653C 10/20 mg over atorvastatin 40 mg at a one-sided 2.5% alpha-level. The overall power to succeed on at least one hypothesis is 99% at a 2.5% alpha-level with 88% power to succeed for both hypotheses.

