### 9.6.1 Statistical Methods for Efficacy Analyses

This section describes the statistical methods that address the primary and secondary objectives.

The study's estimand is a hypothetical estimand that seeks to estimate efficacy as if all participants were to take study medication for 12 weeks.

The estimand consists of the following elements:

- Target population: Participants with hypercholesterolemia (age 18 to 80 years, inclusive), consistent with the study's inclusion/exclusion criteria.
- Variable: Percent change from baseline in LDL-C at Week 12.
- Intercurrent event: Data obtained after discontinuation of treatment are not relevant to this estimand.
- Population level-summary: Difference in variable means comparing randomized treatments (within each cohort).

Analyses will thus exclude measurements collected more than 5 days after the last dose of study treatment.

For the analyses of percent change from baseline in LDL-C at Week 12 in both cohorts, a constrained longitudinal data analysis (cLDA) method proposed by Liang and Zeger will be used [Liang, Kung-Yee and Zeger, Scott L. 2000]. Within each baseline disease risk category (i.e., stratum), this model assumes a common mean across treatment groups at baseline and a different mean for each treatment at each of the post-baseline time points. In this model, the response vector consists of baseline and the values (percent change) observed at each post-baseline time point. Time is treated as a categorical variable so that no restriction is imposed on the trajectory of the means over time. The analysis model will adjust for time and the interaction of time by treatment, and time by baseline disease risk category given in Section 4.1. The treatment difference in terms of mean change from baseline to Week 12 will be estimated and tested from this model. An unstructured covariance matrix will be used to model the correlation among repeated measurements.

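### Section 9.10 sets out to judge whether the treatment effect is consistent across subgroups but plans no contrast between subgroup categories

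*Combined protocol and SAP*

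**What the plan says.** Section 9.10 gives a purpose and a method in one sentence. The purpose and the quantity to be reported are: "To determine whether the treatment effect is consistent across various subgroups, the estimate of the between-group treatment effect (with a nominal 95% CI"). The unit of estimation follows: this quantity "for the primary endpoints will be estimated within each category of the following classification variables". Four variables are listed: age cut at 65, "Gender (male, female"), baseline LDL-C cut at its median, and disease risk category.

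The section names no interaction term, no interval for a difference between categories, and no rule for reading the within-category intervals. It does not mention cohorts. The primary estimand in section 9.6.1 is a "Difference in variable means comparing randomized treatments (within each cohort"), and section 9.10 speaks of primary endpoints in the plural, so analysis by cohort is the natural reading, but it is an inference.

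The planning figures are in section 9.9. On sample size: "162 participants (81 per arm) in Cohort A and 242 participants (121 per arm) in Cohort B will be available for the power calculation". On effect: "the treatment difference in percent changes from baseline in LDL-C at Week 12 are 12.3% and 10.5" percentage points for Cohorts A and B. The standard deviations there are 22 and 23.

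**The concern.** Whether an effect is consistent across two categories depends on the difference between the two category effects. The plan reports the two effects and leaves the reader to compare them by eye. A natural but poor comparison is to ask which intervals exclude zero. A half-cohort has much less power than the whole cohort, so an effect that is identical in both halves will often reach significance in one and miss it in the other. The opposite error is also possible: two wide, overlapping intervals can hide a real difference.

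The primary conclusion is not at stake. What is at stake is any statement in the study report that the effect does or does not hold in, say, older participants or one sex.

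**Working it through.** **Inputs.** From section 9.9: Cohort A, 81 per arm, difference 12.3, SD 22; Cohort B, 121 per arm, difference 10.5, SD 23. Allocation is 1:1 (section 9.1).

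**Step 1. Reproduce the plan's power.** SE = SD × √(2/n); power = Φ(difference/SE − 1.96).
- A: SE = 22 × √(2/81) = 3.457; Φ(3.558 − 1.96) = 94.5% (stated 93%).
- B: SE = 23 × √(2/121) = 2.957; Φ(3.551 − 1.96) = 94.4% (stated 95%).
- Half-widths 1.96 × SE are 6.8 and 5.8 (stated 7.0 and 5.7).

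The agreement is close enough to proceed.

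**Step 2. Power in one half of a cohort.** Assume equal halves and the same true effect in both. Baseline LDL-C is split at its median, so about half of the participants fall in each category; the age and gender shares are not given.
- A: SE = 22 × √(2/40.5) = 4.889; noncentral t power 70.0%.
- B: SE = 23 × √(2/60.5) = 4.182; noncentral t power 70.2%.

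**Step 3. How often exactly one of the two intervals excludes zero.** With p = 0.70:
- both exclude zero: p² = 49%;
- exactly one does: 2p(1 − p) = 2 × 0.70 × 0.30 = 42%;
- neither does: (1 − p)² = 9%.

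**Step 4. Uneven splits.** Exactly one interval excludes zero with probability p₁(1 − p₂) + p₂(1 − p₁).

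| Split | Power, larger part | Power, smaller part | Exactly one excludes zero |
|---|---|---|---|
| 60:40 | 78% | 60% | 44% |
| 70:30 | 84% | 48–48.5% | 51% |
| 80:20 | 88.5% | 34% | 62% |

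**Step 5. Six two-way splits (three factors, two cohorts).** The three splits within a cohort use the same participants, so this was simulated, with random 50:50 splits and t intervals. About 2.5 of the six are discordant on average, and at least one is in about 88% to 89% of trials.

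**Step 6. Other readings of the same intervals, equal halves.** Non-overlapping intervals occur in 0.6% of splits and point estimates of opposite sign in 1.2%.

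**Step 7. The direct contrast.** SE = √2 × SE of one half.
- A: √2 × 4.889 = 6.914; 95% half-width 1.96 × 6.914 = 13.6 points.
- B: √2 × 4.182 = 5.914; half-width 11.6 points.
- False signal with identical effects: 5% by construction (5.0% to 5.3% in simulation).
- Power if the full planned effect is present in one half and absent in the other: Φ(12.3/6.914 − 1.96) = 43% in A; Φ(10.5/5.914 − 1.96) = 43% in B.

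**Sensitivity of the 42%.** The SDs implied by the stated half-widths (22.7 and 22.6) give 43% in A and 40% in B. Using all randomised participants (90 and 135 per arm) gives 37%. Assuming that baseline adjustment works with a correlation of 0.3 to 0.4 gives 35% to 38%; the documents give no such correlation.

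**The case against.** The strongest objection is that the 42% belongs to a reading rule that the plan does not contain. Section 9.10 never says that one interval excluding zero and the other not means inconsistency, and other readings of the same output give about 1% or less (step 6). This stands: 42% is the rate of one common misreading, not the error rate of a planned test. It does not rescue the section, because having neither a contrast nor a rule is the gap itself.

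Second, the analysis is descriptive. The intervals are labelled nominal, subgroups lie outside the Hochberg procedure in section 9.8, and section 9.6 urges caution about nominal p-values in other efficacy analyses. This limits the weight of the point but supplies no contrast.

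Third, section 9.6.1 defers model details to a supplemental SAP that is not available here, and estimation inside each category does not necessarily mean separate fits. Both are fair. But nothing in the text promises a between-category contrast there.

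Fourth, the contrast is weak: its half-width exceeds the whole assumed effect in each cohort, and a non-significant result could itself be misread as consistency. This stands and shapes the fix.

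Stronger readings that a reader might infer are not supported:
- That a discordant pair is the likeliest outcome. With equal halves, both intervals excluding zero is likelier (49% against 42%).
- That the chance of at least one discordant split is 1 − 0.58⁶ = 96%. That treats splits of the same participants as independent.
- That labelling would go wrong. Section 2.1 says only that the data will support marketing authorization in China; nothing ties labelling to subgroup results.

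**Conclusion.** The point holds in a limited form. Section 9.10 states an aim about consistency and specifies an output that does not estimate it.

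If intervals are read by whether they exclude zero, an identical effect gives a discordant pair in about 42% of equal two-way splits, and 44% to 62% for 60:40 to 80:20 splits. This rests on four assumptions: that reading rule, separate analysis of the cohorts, the planning figures in section 9.9, and an identical true effect. If the cohorts were instead pooled (assumed about 202 per arm, difference 11.2, SD 22.6), the rate would be about 11%.

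The change is worth making because it costs almost nothing. It does not affect the primary test, its error control or the sample size.

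**What to change.** In section 9.10, for each factor and each cohort, add the Week 12 treatment-by-subgroup contrast with its 95% interval. Take it from the planned cLDA model extended with subgroup-by-time and treatment-by-subgroup-by-time terms. For risk category the model already has the category-by-time term, so only the three-way term is new. Report the contrast beside the within-category estimates.

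State two reading rules:
- a statement on consistency rests on the size and interval of the contrast, not on which within-category intervals exclude zero;
- a contrast interval that covers zero does not establish consistency.

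Section 9.10 should also say explicitly that the subgroup analysis is done by cohort. Combining cohorts or merging risk levels is optional and does not follow from this gap.

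The cost is SAP wording, a few model contrasts and an extra column in the subgroup tables, with no new data. Section 9 allows changes to non-confirmatory analyses to be documented in the supplemental SAP before unblinding. The drawback is the low precision shown in step 7, which the second reading rule makes plain to the reader.

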## 9.11 Compliance (Medication Adherence)

As part of the routine recording of the amount of study treatment taken by each participant, the number of tablets remaining in trial packaging will be counted, reviewed, and recorded at regular intervals. These results will be used to calculate participant compliance.

A day within the trial will be considered an “On-Therapy” day if the participant in Cohort A takes two tablets OR the participant in Cohort B takes three tablets every day: 1 (for Cohort A) or 2 (for Cohort B) tablets from the bottle and 1 tablet from the blister, as described in Section 8.1.8.

For each participant, percent compliance will then be calculated using the following formula:

$$\text{Compliance (\%)} = \frac{\text{Number of days on therapy}}{\text{Number of days in the double-blind treatment period}} \times 100.$$

The “Number of days in the double-blind treatment period” is the total number of days from the first dose of study medication to the last dose of study medication.

Summary statistics will be provided on percent compliance by treatment group for the FAS population.

### **9.12 Extent of Exposure**

The Extent of Exposure to study treatment will be evaluated by summary statistics for the “Number of Days on Therapy” by treatment group.

## 10 SUPPORTING DOCUMENTATION AND OPERATIONAL CONSIDERATIONS

### 10.1 Appendix 1: Regulatory, Ethical, and Study Oversight Considerations

#### 10.1.1 Code of Conduct for Clinical Trials

Merck Sharp and Dohme Corp., a subsidiary of Merck & Co., Inc. (MSD)

#### Code of Conduct for Interventional Clinical Trials

##### I. Introduction

###### A. Purpose

MSD, through its subsidiaries, conducts clinical trials worldwide to evaluate the safety and effectiveness of our products. As such, we are committed to designing, implementing, conducting, analyzing and reporting these trials in compliance with the highest ethical and scientific standards. Protection of participants in clinical trials is the overriding concern in the design of clinical trials. In all cases, MSD clinical trials will be conducted in compliance with local and/or national regulations (eg, International Council for Harmonisation Good Clinical Practice [ICH-GCP]) and in accordance with the ethical principles that have their origin in the Declaration of Helsinki.

###### B. Scope

Highest ethical and scientific standards shall be endorsed for all clinical interventional investigations sponsored by MSD irrespective of the party (parties) employed for their execution (eg, contract research organizations, collaborative research efforts). This Code is not intended to apply to trials that are observational in nature, or which are retrospective. Further, this Code does not apply to investigator-initiated trials, which are not under the full control of MSD.

##### II. Scientific Issues

###### A. Trial Conduct

###### 1. Trial Design

Except for pilot or estimation trials, clinical trial protocols will be hypothesis-driven to assess safety, efficacy, and/or pharmacokinetic or pharmacodynamic indices of MSD or comparator products.

Alternatively, MSD may conduct outcomes research trials, trials to assess or validate various endpoint measures, or trials to determine patient preferences, etc.

The design (ie, participant population, duration, statistical power) must be adequate to address the specific purpose of the trial. Participants must meet protocol entry criteria to be enrolled in the trial.

###### 2. Site Selection

MSD selects investigative sites based on medical expertise, access to appropriate participants, adequacy of facilities and staff, previous performance in clinical trials, as well as budgetary considerations. Prior to trial initiation, sites are evaluated by MSD personnel to assess the ability to successfully conduct the trial.

###### 3. Site Monitoring/Scientific Integrity

Investigative trial sites are monitored to assess compliance with the trial protocol and general principles of Good Clinical Practice (GCP). MSD reviews clinical data for accuracy, completeness, and consistency. Data are verified versus source documentation according to standard operating procedures. Per MSD policies and procedures, if fraud, scientific/research misconduct, or serious GCP-noncompliance is suspected, the issues

are investigated. When necessary, the clinical site will be closed, the responsible regulatory authorities and ethics review committees notified.

### **B. Publication and Authorship**

Regardless of trial outcome, MSD commits to publish primary and secondary results of its registered trials of marketed products in which treatment is assigned, according to the prespecified plans for data analysis. To the extent scientifically appropriate, MSD seeks to publish the results of other analyses it conducts that are important to patients, physicians, and payers. Some early phase or pilot trials are intended to be hypothesis-generating rather than hypothesis testing, in such cases, publication of results may not be appropriate since the trial may be underpowered and the analyses complicated by statistical issues such as multiplicity.

MSD's policy on authorship is consistent with the recommendations published by the International Committee of Medical Journal Editors (ICMJE). In summary, authorship should reflect significant contribution to the design and conduct of the trial, performance or interpretation of the analysis, and/or writing of the manuscript. All named authors must be able to defend the trial results and conclusions. MSD funding of a trial will be acknowledged in publications.

## **III. Participant Protection**

### **A. Ethics Committee Review (Institutional Review Board [IRB]/Independent Ethics Committee [IEC])**

All clinical trials will be reviewed and approved by an IRB/IEC before being initiated at each site. Significant changes or revisions to the protocol will be approved by the ethics committee prior to implementation, except changes required urgently to protect participant safety that may be enacted in anticipation of ethics committee approval. For each site, the ethics committee and MSD will approve the participant informed consent form.

### **B. Safety**

The guiding principle in decision-making in clinical trials is that participant welfare is of primary importance. Potential participants will be informed of the risks and benefits of, as well as alternatives to, trial participation. At a minimum, trial designs will take into account the local standard of care.

All participation in MSD clinical trials is voluntary. Participants enter the trial only after informed consent is obtained. Participants may withdraw from an MSD trial at any time, without any influence on their access to, or receipt of, medical care that may otherwise be available to them.

### **C. Confidentiality**

MSD is committed to safeguarding participant confidentiality, to the greatest extent possible. Unless required by law, only the investigator, Sponsor (or representative), ethics committee, and/or regulatory authorities will have access to confidential medical records that might identify the participant by name.

